Ototoxicity has been observed in up to 31% of patients treated with a single dose of cisplatin (50 mg/m^2) and is manifested by tinnitus and/or hearing loss in the high frequency range (4000 to 8000 Hz). Decreased ability to hear normal conversational tones may occur occasionally. Ototoxicity can be more severe in children than in adults and more frequent and severe with repeated administration. Hearing loss can be unilateral or bilateral and is usually not reversible. During treatment with cisplatin, it is necessary to monitor hearing at each visit. An audiogram is recommended after a cumulative dose of 360 mg/m^2. Subsequent doses of cisplatin should not be given until an audiometric analysis indicates that auditory acuity is within normal limits.

- **Myelosuppression**

Myelosuppression occurs in 25% to 30% of patients treated with cisplatin. The nadirs in circulating platelets and leukocytes occur between days 18 and 23, with most patients recovering by day 39. Leukopenia and thrombocytopenia are more pronounced at higher doses (>50 mg/m^2). Anemia (a decrease in hemoglobin of 2 g/100 ml) occurs at approximately the same frequency and with the same timing as leukopenia and thrombocytopenia.

- **Neurotoxicity**

Cisplatin neurotoxicity is characterized by peripheral neuropathies, which are sensory in nature but can also include motor difficulties such as reduced deep-tendon reflexes and leg weakness. The symptoms usually occur after prolonged therapy (4 to 7 months). Cisplatin therapy should be discontinued when serious neuropathy develops. The neuropathy, however, may progress further even after discontinuation of treatment.

In the DF/HCC neoadjuvant trial of 4 cycles of cisplatin 75mg/m^2 q21 days in 28 women with triple negative breast cancer, only one grade 4 toxicity was observed, an elevation in SGOT. There were 7 grade 3 symptomatic toxicities: one each, fatigue, abdominal pain, GI toxicity unspecified, myalgias, skin toxicity and tinnitus. Grade 3 toxicities in laboratory tests were seen in 2 women with low white blood cells and one each hyperkalemia and elevation in SGPT.

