#### **4.1.2 Dose Limiting Toxicity**

Toxicity will be graded using the NCI Common Terminology Criteria for Adverse Events (NCI CTCAE) Version 3.0. Dose-limiting toxicity (DLT) is defined as the following study drug-related events experienced during Cycle 1:

- Grade 4 thrombocytopenia.
- Grade 4 neutropenia lasting >5 days.
- Febrile neutropenia (ANC <1.0 x10^9/L with fever ≥38.5°C).
- Treatment delay of >2 weeks.

- Other Grade 3 non-haematological toxicities; excluding non-optimally treated nausea, vomiting and diarrhea

Patients with dose-limiting toxicity after cycle 1 who have documented clinical benefit (stable disease or an objective response) may continue to be treated at a reduced dose level if considered clinically appropriate by the investigator.

Any patient in whom a DLT occurs during any cycle will have his or her treatment delayed until toxicity resolves to grade 1 or below.

[figure not shown]

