#### **4.5.3.8 Management of Non-hematologic treatment related adverse events attributable to cisplatin**

Any cisplatin related toxicity, with the exception of ototoxicity, should resolve to  $\leq$  Grade 1 prior to retreatment with cisplatin. Treatment with cisplatin may be continued on Day 1 of each cycle as long as each of the following criteria are met:

- ANC  $>1.5 \times 10^9/L$
- Platelets  $>100 \times 10^9/L$
- Creatinine  $\leq 1.5$  mg/dL
- CrCl  $>50$  mL/min (Creatinine Clearance should be calculated every cycle)
- Neurotoxicity  $\leq$  CTCAE grade 1

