## Ototoxicity

Ototoxicity has been observed in up to 31% of patients treated with a single dose of cisplatin ( $50 \text{ mg/m}^2$ ) and is manifested by tinnitus and/or hearing loss in the high frequency range (4000 to 8000 Hz.) Decreased ability to hear normal conversational tones may occur occasionally. Ototoxicity can be more severe in children than in adults and more frequent and severe with repeated administration. Hearing loss can be unilateral or bilateral and is usually not reversible. During treatment with cisplatin, it is necessary to monitor hearing at each visit. Audiometric testing should be performed at baseline, at the end of the 2nd, 4th and 6th cycles of cisplatin and as clinically indicated thereafter. A final audiogram should be done at study completion. In the event that cisplatin is permanently discontinued, only the final audiometric test done at study completion is required, unless otherwise clinically indicated.

If Grade  $\geq$ 2 ototoxicity develops:

If a patient had an initial dose level of  $75 \text{ mg/m}^2$  cisplatin, reduce the cisplatin to  $60 \text{ mg/m}^2$ . If the patient had an initial dose level of  $60 \text{ mg/m}^2$  cisplatin, at the investigators discretion, the cisplatin can be reduced to  $50 \text{ mg/m}^2$ .

AZD2281 dose adjustment is not necessary

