Other clinically significant grade $\geq 3$ toxicities	Hold up to 28 days until recovery to $\leq$ grade 1 or baseline if considered possibly related; reduce dose as per Table 7. After resumption, if toxicity returns interrupt. If toxicity does not recover to $\leq$ grade 1, discontinue AZD2281. The minimum dose of AZD2281 is 50 mg bid days 1-3 of a 21 day cycle for patients treated with intermittent dosing and 50 mg bid for patients treated with continuous dosing.	Hold up to 14 days until recovery to $\leq$ grade 1 or baseline if considered possibly related; may resume at current dose or with dose reduction, to a minimum of 60 mg/m  , per the Investigator’s discretion
Grade 4 non-hematologic toxicities attributable to cisplatin	No change unless cisplatin is discontinued. If cisplatin is discontinued, at the investigators discretion and if treatment criteria are met, dose of AZD2281 can be escalated to 400 mg bid continuously.	Discontinue cisplatin. If the investigator believes that the patient is benefiting from combination therapy then reducing cisplatin to 50 mg/m  and maintaining the dose of AZD2281 may be considered instead of the above after discussion with the Principal Investigator and agreed by AstraZeneca.

a The dose reductions advised in the table relate to patients who had an initial cisplatin dose of 75mg/m^2, for those patients that had their initial cisplatin dose administered at 60 mg/m^2, the dose modification of cisplatin should be a reduction to 50 mg/m^2 per the Investigator’s discretion.

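### For Grade 2–3 hearing loss the cisplatin action is keyed to the starting dose, so a 75 mg/m² starter already at 60 gets no reduction, hold or stop under Section 4.5.3.8

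*Protocol*

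**What the plan says.** **Ototoxicity action.** For Grade 2 or worse, the Ototoxicity paragraph of Section 4.5.3.8 begins "If a patient had an initial dose level of" 75 mg/m² and sends that patient to 60. A patient who began at 60 may go to 50 at the investigator's discretion. The AZD2281 dose is left alone. Table 8 shows 60 as the target, and its footnote a explains: "The dose reductions advised in the table relate to patients who had an initial cisplatin dose of" 75 mg/m², with 50 as the discretionary target for 60 starters.

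**Recovery before retreatment.** Section 4.5.3.8 opens with "Any cisplatin related toxicity, with the exception of ototoxicity, should resolve to" Grade 1 or lower before cisplatin is given again. The Ototoxicity paragraph also says "Hearing loss can be unilateral or bilateral and is usually not reversible", and describes the toxicity as more frequent and severe with repeated dosing.

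**Other statements that touch hearing.** Section 4.1.2 says DLT "is defined as the following study drug-related events experienced during Cycle 1", and lists Grade 3 non-haematological events among them. It then says: "Any patient in whom a DLT occurs during any cycle will have his or her treatment delayed until toxicity resolves to grade 1" or below. A patient with DLT after cycle 1 and documented benefit "may continue to be treated at a reduced dose level if considered clinically appropriate by the investigator". Section 2 (Cisplatin toxicity) says: "Subsequent doses of cisplatin should not be given until an audiometric analysis indicates that auditory acuity is within normal limits".

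**Creatinine clearance.** For values below 50 mL/min, the Nephrotoxicity paragraph of Section 4.5.3.8 says to hydrate and hold. The Table 8 row says the same and adds a restart at 60 mg/m².

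**The concern.** A dose-modification rule should say what to do from the dose the patient is now receiving. This one looks back to the dose at entry. Once a 75 starter is at 60, the instruction for new or worse hearing loss is to reduce to 60, which changes nothing. Most other cisplatin toxicities would still force a pause, because they must recover before the next dose. Hearing loss is expressly excused from that.

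Two things are at stake. One is avoidable harm of a kind the Protocol itself calls usually irreversible. The other is uneven practice: two sites could treat the same patient differently, one continuing at 60 and the other waiting for a recovery that is unlikely to come, which in practice ends cisplatin.

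**Working it through.** The plan gives no figure to reproduce, so the check applies the written rule to each possible dose.

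**Inputs.** Targets come from the Ototoxicity paragraph of Section 4.5.3.8 and Table 8 footnote a: start at 75, target 60; start at 60, target 50 (discretionary).

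**Formula.** Change (%) = 100 × (target − current) / current.

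| Starting dose | Current dose | Target | Change |
|---|---|---|---|
| 75 | 75 | 60 | (60 − 75)/75 = −20.0% |
| 75 | 60 | 60 | (60 − 60)/60 = 0.0% |
| 75 | 50 | 60 | (60 − 50)/50 = +20.0% |
| 60 | 60 | 50 | (50 − 60)/60 = −16.7% |
| 60 | 50 | 50 | (50 − 50)/50 = 0.0% |

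The second row is the gap. The third arises if the patient has dropped to 50 under Section 4.5.2.2. No investigator would raise the dose there, but it shows that the keying is at fault. The last row is the same gap one level lower.

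**How a 75 starter reaches 60.** Through an earlier event in Table 8, or through the cisplatin reductions that Tables 6 and 7 prescribe on some 50 mg bid intermittent schedules.

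**Whether another rule supplies the next step.**
- Section 4.5.2.2 allows 50, but for a 75 starter only after four completed cycles at the full 75. A patient reduced earlier does not qualify.
- The Table 8 row for other Grade 3 or worse toxicities stops at 60, and hearing has its own row.
- The Grade 4 row discontinues cisplatin, or allows 50 by agreement, but covers Grade 4 only.

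**Illustration (my assumptions: six cycles; reduction to 60 after cycle 2 for nausea; new Grade 2 hearing loss on the cycle 4 audiogram, one of the scheduled ones).** Cumulative cisplatin to cycle 6:
- rule as written: 2×75 + 4×60 = 390 mg/m²
- step to 50 for cycles 5 and 6: 2×75 + 2×60 + 2×50 = 370 mg/m²
- stop after cycle 4: 2×75 + 2×60 = 270 mg/m²

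The written rule gives 20 mg/m² more than a step to 50, and 120 mg/m² more than stopping.

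**Hearing statements side by side.**

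| Grade | Section 4.5.3.8 and Table 8 | Section 4.1.2 | Section 2 (background) |
|---|---|---|---|
| 2 | Target by starting dose; no recovery needed | Does not apply | Wait for normal acuity |
| 3 | Same as Grade 2 | Arguably delay to Grade 1 or below | Wait for normal acuity |
| 4 | Discontinue cisplatin, exception by agreement | As Grade 3, but overtaken by the discontinuation | Overtaken by the discontinuation |

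Section 4.1.2 confines DLT to Cycle 1 by definition, yet twice uses the term for later cycles. A patient already at 60 for toxicity is past Cycle 1, so whether the delay applies to that patient depends on which usage prevails.

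**The case against.** **Investigator judgement already covers this.** The Synopsis (Duration of treatment), Table 4 footnote h and the note under Figure 3 make continued treatment conditional on benefit and on freedom from significant or unacceptable toxicity. Section 4.1.1 lets either agent be reduced, Section 4.4.6.1 allows discontinuation for an adverse event, and Section 5.1.3 foresees stopping for hearing loss. This stands to a point. A reader might infer that the Protocol obliges a patient with worsening hearing to continue at 60, and it does not. But these provisions give no trigger for hearing loss, and the 28-day criterion in Section 4.4.6.1 covers Grade 3–4 only, so it misses new Grade 2 loss.

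**A fixed target avoids ratcheting.** A rule keyed to the current dose could cut cisplatin every cycle for the same stable Grade 2 loss, and 60 may be the intended floor. That is a fair design reason. It argues for a trigger limited to new or worse loss, and for stating the floor and what follows from it.

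**The hearing conflict is narrow.** A reader might infer that three rules contradict each other at every grade. They do not. Section 2 is background. The Ototoxicity paragraph repeats most of that text but puts the study's audiometry schedule in place of the normal-acuity sentence, which suggests that Section 4.5.3.8 was meant to supersede it. Section 4.1.2 cannot reach Grade 2, and at Grade 3 the specific exemption for ototoxicity would ordinarily prevail over the general delay rule. What remains is an arguable conflict at Grade 3 and a background sentence left in directive wording.

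**The same keying appears for nausea and creatinine clearance.** A reader might infer an equal gap there. The documents do not support that: nausea and vomiting must recover to Grade 1 or lower, and low clearance triggers a hold until it exceeds 50 mL/min.

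**The clearance text is not contradictory.** A site that follows Table 8 satisfies both statements. The risk is a site that reads only the paragraph and restarts at 75.

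**Conclusion.** The concern holds for Grade 2–3 ototoxicity. Read literally, Section 4.5.3.8 and Table 8 give a 75 starter already at 60 a 0% reduction for new or worse hearing loss, with no hold and no stop. The only backstop is general investigator judgement. At Grade 3 the instructions arguably diverge between Sections 4.1.2 and 4.5.3.8. The missing restart dose in the Nephrotoxicity paragraph is a separate, smaller inconsistency.

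This is a minor to moderate safety clarification. The patients affected are few: mainly 75 starters reduced before completing four full-dose cycles who then have a further hearing event. The Protocol gives no rate for such events. Its figure of up to 31% is ungraded and follows a single 50 mg/m² dose, so it should not be read as the frequency of this problem.

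A reader might also infer that dose finding is compromised. It is not: the gap arises only after an earlier reduction, and Cycle 1 DLT and MTD determination do not depend on it.

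**What to change.** - Key the ototoxicity action in Section 4.5.3.8 and Table 8 to the dose at the time of the event, and trigger it only on a new or worse grade.
- State that a patient already at 60 discontinues cisplatin or, if the sponsor's physicians prefer, steps to 50. The latter is −16.7% from 60, and (50 − 75)/75 = −33.3% from 75.
- State that Section 4.5.3.8 governs hearing over Sections 2 and 4.1.2, and give an explicit action for Grade 3.
- Add the 60 mg/m² restart dose to the Nephrotoxicity paragraph.
- Use the same current-dose wording for nausea/vomiting and creatinine clearance, for consistency only.

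The cost is a few lines in Table 8 and the adjoining paragraphs. The downside is that some patients receive less cisplatin or stop it earlier.

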**4.5.3.9 Management of toxicity of AZD2281 (monotherapy treatment)**

Any toxicity observed during the course of the study could be managed by interruption of the dose if deemed appropriate by the Investigator. Repeat dose interruptions are allowed as required, for a maximum of 14 days on each occasion. If the interruption is any longer than this the AstraZeneca study team must be informed. AZD2281 must be interrupted until the patient recovers completely or the toxicity reverts to the National Cancer Institute (NCI) Common Terminology Criteria for Adverse Events (current version) grade 1 or less.

Where toxicity reoccurs following re-challenge with AZD2281, and where further dose interruptions are considered inadequate for management of toxicity, then the patient should be considered for dose reduction or must permanently discontinue treatment with AZD2281.

Treatment must be interrupted if any NCI-CTCAE grade 3 or 4 adverse event occurs which the Investigator considers to be related to administration of AZD2281.

**Management of leukopenia and/or anaemia:**

An exception to the management of olaparib-related toxicity is the occurrence of leukopenia and/or anaemia. In this case, the AE should be managed as deemed appropriate by the investigator (eg G-CSF or blood transfusions), without interruption in study drug or change in dose. However, growth factors must be discontinued once the AE has recovered to CTCAE grade 1 or better. They may be resumed, if necessary, if leukopenia/anaemia develops again and discontinued once it recovers.

**Management of prolonged haematological toxicities including anaemia, neutropenia or thrombocytopenia whilst on study treatment:**

If any study treatment is interrupted/delayed because of one or more of the following:

- ≥2 week interruption/delay in study treatment due to CTC grade >2 neutropenia
- ≥2 week interruption/delay in study treatment due to CTC grade >2 thrombocytopenia
- ≥2 week interruption/delay in study treatment due to CTC grade >2 anaemia and or development of blood transfusion dependence

Weekly blood counts should be performed during the study treatment interruption/delay. If the levels have still not recovered to CTC Grade ≤1 after 4 weeks of dose interruption, the patient should be referred to a haematologist for further investigations. Bone marrow analysis or blood cytogenetic analysis should be considered at this stage according to standard haematological practice. Development of myelodysplastic syndrome should be reported as an SAE and full reports must be provided by the Investigator for documentation on the Patient Safety database.

The dose of AZD2281 must not be adjusted under any other circumstances unless the AstraZeneca Study Physician gives prior agreement.

*Management of new or worsening pulmonary symptoms:* If new or worsening pulmonary symptoms (e.g. dyspnoea) or radiological abnormality occurs, an interruption in olaparib dosing is recommended and a diagnostic workup (including a high resolution CT scan) should be performed, to exclude pneumonitis. Following investigation, if no evidence of abnormality is observed on CT imaging and symptoms resolve, then olaparib treatment can be restarted, if deemed appropriate by the investigator. If significant pulmonary abnormalities are identified, these need to be discussed with the AstraZeneca Study Physician.

All dose reductions and interruptions (including any missed doses), and the reasons for the reductions/interruptions are to be recorded in the CRF (up to the data cut-off).

████████████████████  
AZD2281 should be stopped before surgery and re-started after wound has healed following recovery.

No stoppage of AZD2281 is required for any biopsy procedures.

AZD2281 should be discontinued for a minimum of 7 days before a patient undergoes therapeutic palliative radiation treatment.

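### In the monotherapy phase, olaparib-related anaemia is managed without stopping the drug, so the haematology work-up for prolonged anaemia, which runs only on interruption time, is never reached

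*Protocol*

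**What the plan says.** Section 4.5.3.9 of the protocol governs toxicity once the patient is on AZD2281 alone. Its general rule for drug-related severe events is "Treatment must be interrupted if any NCI-CTCAE grade 3 or 4 adverse event occurs".

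The paragraph on leukopenia and/or anaemia is an express exception. The investigator manages these events, for example with G-CSF or transfusion, "without interruption in study drug or change in dose". No grade ceiling is given. Where growth factors are used, "growth factors must be discontinued once the AE has recovered to CTCAE grade 1 or better".

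The following block is headed "Management of prolonged haematological toxicities including anaemia, neutropenia or thrombocytopenia whilst on study treatment". It opens with "If any study treatment is interrupted/delayed because of one or more of the following". Its anaemia trigger is a two-or-more "week interruption/delay in study treatment due to CTC grade >2 anaemia and or development of blood transfusion dependence". Two actions follow. The first is "Weekly blood counts should be performed during the study treatment interruption/delay". The second is referral to a haematologist, with marrow or cytogenetic analysis to be considered; its condition is "If the levels have still not recovered to CTC Grade ≤1 after 4 weeks of dose interruption".

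**The concern.** The two adjacent paragraphs do not fit together. The first tells the site not to interrupt for olaparib-related anaemia; the second names anaemia but measures everything in interruption time. A site that obeys the first cannot satisfy the second.

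The step that is lost matters. Section 2 lists MDS/AML among the events reported with olaparib in heavily pretreated patients, and Section 4.4.6.1 makes marrow findings of MDS/AML a ground for discontinuation. Under Section 4.2.3, patients may enter monotherapy after six cycles of cisplatin and take 400 mg bid. Persistent anaemia supported by transfusion while dosing continues is a case in which a haematology opinion would be wanted, and this block is the only rule in the protocol that directs one.

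**Working it through.** There is no stated figure to reproduce. The check is a trace of the decision path, followed by a count of scheduled blood tests.

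**Path for persistent Grade >2 olaparib-related anaemia on monotherapy**

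| Step in the work-up | What it requires | What a site following the exception has |
|---|---|---|
| Lead-in | treatment interrupted or delayed | not interrupted |
| Anaemia trigger | at least 2 weeks of interruption/delay | 0 weeks |
| Weekly counts | run during the interruption/delay | none triggered |
| Haematology referral | 4 weeks of dose interruption | 0 weeks |

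Cisplatin has stopped, so AZD2281 is the only study treatment left and a cisplatin delay cannot open the path. The transfusion-dependence wording may be meant as a separate trigger. It still sits under the same lead-in, and the counts and referral clock still run on interruption time.

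**Other places that might restore the step**

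- Section 5.6.1 permits marrow or cytogenetic samples for prolonged toxicity as defined in Section 4.5.3, which leads back to the same block.
- Section 4.4.6.1 allows, but does not require, discontinuation for Grade 3-4 events unresolved at 28 days. It orders no counts and no referral.
- Section 4.4.6.2 asks for general evaluation after discontinuation and names no referral.
- Table 6 covers anaemia during combination therapy only.

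**Scheduled counts**

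Assumptions: a hold, had there been one, would start on the day of detection; the work-up's weekly counts begin once the 2-week entry condition is met; visit windows are ignored. The work-up then gives counts at +21 and +28 days, and at +14 if the entry day is counted: 2 to 3 by day 28.

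Section 4.2.3 and Table 5 place visits at Days 1, 8, 15, 22 and 43, then every 42 days (43 + 42 = 85; 85 + 42 = 127). Scheduled counts from +14 to +28 days after detection are:

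| Anaemia first seen | Window | Scheduled visits in window | Number |
|---|---|---|---|
| Day 1 | 15–29 | 15, 22 | 2 |
| Day 8 | 22–36 | 22 | 1 |
| Day 15 | 29–43 | 43 | 1 |
| Day 22 | 36–50 | 43 | 1 |
| Day 43 | 57–71 | none | 0 |
| Day 85 | 99–113 | none | 0 |

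Scheduled gaps are 43 − 22 = 21 days and then 85 − 43 = 42 days. From Day 43 onward the next scheduled count falls 42 − 28 = 14 days after the four-week point.

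Under the alternative schedule in Table 4, footnote h, weekly visits give 3 counts in the window (+14, +21, +28), so none is lost. Once visits become four-weekly after week 8, the number is 1 (+28).

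**The case against.** The strongest reply is that the exception is not an absolute bar. It is worded as guidance and leaves management to the investigator, and Section 4.5.3.9 opens by allowing any toxicity to be handled by interruption. The work-up itself envisages a hold for anaemia above Grade 2. On that reading, ordinary anaemia is supported on drug, while prolonged severe anaemia may be held and so reaches the work-up. Section 4.4.6.1 also provides a 28-day criterion that does not depend on a hold and coincides with the referral point.

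Part of this stands. The protocol plainly expects some holds for anaemia, and the bypass does not occur where the investigator departs from the exception, where the drug is held for another reason, or where the anaemia is not attributed to olaparib. However, nothing in the text tells the investigator when to move from the exception to a hold, and the 28-day criterion is optional and names no referral.

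It is also fair that the loss of monitoring is partial. Section 5.6.1 provides for haematology when clinically indicated and for repeating clinically significant abnormal values. The growth-factor stopping rule in practice needs interim counts, though it does not cover anaemia managed by transfusion. The table above therefore counts scheduled visits only, and extra counts would shorten the gaps. The missing referral does not depend on the visit schedule.

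**Conclusion.** The concern holds. As written, a monotherapy site that follows the anaemia exception never reaches the prescribed weekly counts or the haematology referral for persistent Grade >2 olaparib-related anaemia.

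One of the three work-up triggers, anaemia, is clearly bypassed. Thrombocytopenia is unaffected, and neutropenia is affected only if leukopenia in the exception is read to include it. On scheduled visits alone, the work-up's 2 to 3 counts become 2, 1 or 0 under Table 5, depending on when the anaemia is first seen. The count comparison rests on the timing assumptions stated above; the loss of the referral needs only that the site does not interrupt AZD2281.

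The documents give no figure for how many patients this would concern. It is a patient-safety gap that should be fixed; it has no bearing on the MTD, PK or response-rate results.

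**What to change.** In the prolonged-toxicity block of Section 4.5.3.9, replace interruption time with duration of the cytopenia:

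- start weekly counts after at least 2 weeks of Grade >2 anaemia, neutropenia or thrombocytopenia, or on development of transfusion dependence;
- refer to a haematologist if the count has not recovered to Grade 1 or better 4 weeks from onset;
- state that both apply whether or not AZD2281 is interrupted.

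The no-interruption exception can stay as it is, since keeping anaemic patients on drug is a clinical choice that this change does not disturb. The cost is wording in one section, a few additional local blood counts, and occasional haematology referrals for patients who remain on treatment.
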